4.1.5 Day of SRS

- 4.1.5.1** Documentation of corticosteroid use/no dexamethasone (or any other corticosteroid with the purpose of treating cerebral edema) use.
- 4.1.5.2** Continued fingerstick glucose draws by patient 4 times a day (in the morning before breakfast (fasting), before lunch, before dinner, and before bed) for at least 1 week after SRS.

4.1.6 1 week after SRS (\pm 3 days)

- 4.1.6.1** Review the patient's blood glucose and medication administration logs.
- 4.1.6.2** CBC with differential and CMP including LFTs.
- 4.1.6.3** Fingerstick Glucose draw by nurse/research team member.
- 4.1.6.4** Adverse event evaluation. If no "*concerning toxicity*" or "*serious toxicity*" (see section 5.3.1), then patient will be instructed to only obtain fingerstick glucose draws once a day (in the morning before breakfast [fasting]) until the day of discontinuation of glyburide.
 - 4.1.6.4.1** If the patient does have a "*concerning toxicity*" or "*serious toxicity*" they must discontinue glyburide (see section 5.3.1) and thus can also discontinue with their fingerstick glucose draws.
- 4.1.6.5** Documentation of corticosteroid usage (record the date of initiation, dose and reason for initiation of any new corticosteroid, especially dexamethasone).

4.1.7 1 month after SRS (- 5 or +10 days)

- 4.1.7.1** Discontinue glyburide (last dose is taken the evening of obtaining the follow-up MRI) and discontinue blood glucose monitoring. Have patient return all remaining (untaken) glyburide tablets.
- 4.1.7.2** Follow-up brain MRI with and without contrast. T1-weighted, T2 and/or FLAIR MRI of the brain (maximum slice thickness 5mm). FLAIR imaging is preferred.
 - 4.1.7.2.1** T1 post gadolinium sequence will be imported into the Eclipse treatment planning system and the radiation oncologist will contour the enhancing tumor that received the prescribed dose of SRS.
 - 4.1.7.2.2** FLAIR sequence will be imported into the Eclipse treatment planning system. FLAIR volume will be automatically calculated using "Region

“Growing” on Eclipse (Appendix I). The automated contours will be verified and modified as needed by the radiation oncologist.

- 4.1.7.3** Follow-up history and physical with neurologic examination and corticosteroid use documentation (record the date of initiation, dose and reason for initiation of any new corticosteroid, especially dexamethasone). A last fingerstick glucose draw will be done by the nurse/research team member at this visit.

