4.2.5 Day of SRS

- 4.2.5.1** Documentation of corticosteroid use/no dexamethasone (or any other corticosteroid with the purpose of treating cerebral edema) use.

4.2.5.2 Continued fingerstick glucose draws by patient once a day (in the morning before breakfast [fasting]) for at least 1 week after SRS. Please see section 5.4.2 for further details.

4.2.6 1 week after SRS (± 3 days)

4.2.6.1 Review the patient's blood glucose and medication administration logs.

4.2.6.2 CBC with differential and CMP including LFTs.

4.2.6.3 Fingerstick Glucose draw by nurse/research team member.

4.2.6.4 Adverse event evaluation. If no "*concerning toxicity*" or "*serious toxicity*" (see section 5.3.2), then patient will be instructed to discontinue blood glucose monitoring.

4.2.6.4.1 If the patient does have a "*concerning toxicity*" or "*serious toxicity*" they must discontinue their investigational medication (see section 5.3.2) and thus can also discontinue with fingerstick glucose draws.

4.2.6.5 Documentation of corticosteroid use (record the date of initiation, dose and reason for initiation of any new corticosteroid, especially dexamethasone).

4.2.7 1 month after SRS (- 5 or + 10 days)

4.2.7.1 Discontinue investigational medication (last dose is taken the evening of obtaining the follow-up MRI). Have patient return all remaining (untaken) investigational medication tablets.

4.2.7.2 Follow-up brain MRI with and without contrast. T1-weighted, T2, and/or FLAIR MRI of the brain (maximum slice thickness 5mm). FLAIR imaging is preferred.

4.2.7.2.1 T1 post gadolinium sequence will be imported into the Eclipse treatment planning system and the radiation oncologist (who will be blinded to the patient's investigational medication) will contour the enhancing tumor that received the prescribed dose of SRS.

4.2.7.2.2 FLAIR sequence will be imported into the Eclipse treatment planning system. FLAIR volume will be automatically calculated using "Region Growing" on Eclipse (Appendix I). The automated contours will be verified and modified as needed by the radiation oncologist who will be blinded to the patient's investigational medication.

4.2.7.3 Follow-up history and physical with neurologic examination and corticosteroid use documentation (record the date of initiation, dose and reason for initiation of any new corticosteroid, especially dexamethasone). A last fingerstick glucose draw will be done by the nurse/research team member.

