5.4 Safety and efficacy (blood glucose monitoring)

5.4.1 Pilot Portion

All patients will be provided with a medication/blood glucose log, a blood glucose monitor, and taught to perform self fingerstick glucose draws (see Appendices II-VI). The first blood glucose draw will be done by a nurse or research team member on the visit 5-9 days prior to SRS and the initial value will be recorded in the blood glucose log. Starting at the initiation of glyburide and for at least the first week after SRS, the patient will take and record blood glucose levels 4 times a day (in the morning before breakfast [fasting], before lunch, before dinner, and before bed). After one week post SRS, if the patient does not experience a dose limiting toxicity (DLT, as defined in section 5.3.1), he/she will be instructed to obtain blood glucose levels once a day (in the morning before breakfast [fasting]) until the discontinuation of glyburide. If the patient does experience a DLT then he/she must discontinue glyburide (as per section 5.3.1) and will not have to continue checking their blood glucose levels.

If the patient is symptomatic and this is thought to be attributable to hypoglycemia, he/she should check a fingerstick glucose level and begin “low blood sugar intervention” as described in **Section 5.4.1.1** (also see Appendix IV). If fingerstick glucose levels reach ≤ 80 mg/dl (symptomatic or asymptomatic), the patient should begin “low blood sugar intervention”. If “low blood sugar intervention” does not cause the blood sugar to rise above 80 mg/dl, or if symptoms persist, the patient will be instructed to contact the study team and/or call 911 for emergency services.

5.4.1.1 “Low Blood Sugar Intervention”:

Procedures:

1. Take 15 grams of carbohydrate:
 - a. 3 or 4 glucose tablets or
 - b. 4 oz (1/2 cup) of fruit juice or
 - c. 6 oz regular soda (about 1/2 can)
2. Rest and wait 15 minutes
3. Recheck blood sugar

4. Repeat Steps 1-3 if blood sugar still less than 80 mg/dl
5. If next meal is more than 1 hour away, eat a snack.

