5.4.2 Randomized Portion

5.4.2.1 All patients will be provided with a medication/blood glucose log, a blood glucose monitor, and taught to perform self fingerstick glucose draws (see Appendices II-VI). The first blood glucose draw will be done by a nurse or research team member on the visit 5-9 days prior to SRS and the initial value will be recorded in the blood glucose log.

5.4.2.2 If the Pilot Portion (at either full dose or at one dose reduction) demonstrates no "**serious toxicities**" and ≤ 3 "**concerning toxicities**" (described in section 5.3.1), patients in the Randomized Portion of the trial will be taught and instructed to measure blood glucose levels once a day (in the morning before breakfast (fasting)) starting at the initiation of the investigational medication and continuing for at least the first week after SRS. If no "**concerning toxicities**" or "**serious toxicities**" are found at the one week post SRS visit, then the patient may proceed through the rest of the trial with no further need to assess blood glucose via the fingerstick draws. If the patient does experience a "**concerning toxicity**" or "**serious toxicity**" then he/she must discontinue their investigational medication (as per section 5.3.2) and will not have to continue checking their blood glucose levels.

5.4.2.3 If the Pilot Portion (at either full dose or at one dose reduction) demonstrates no "**serious toxicities**" and 4-5 "**concerning toxicities**" (described in section 5.3.1), patients in the Randomized Portion of the trial will be taught and instructed to measure blood glucose as per section 5.4.1.

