APPENDIX VIII
STUDY SCHEDULE OF EVENTS
PILOT PORTION

Assessments	Pretreatment		Treatment		Post Treatment		
	≤ 60 days prior to registration	≤ 14 days prior to registration	5-9 days prior to SRS	Day of SRS	7 days (1 wk) post SRS (± 3 days)	30 days (1 mo) post SRS (-5 to +10 days)	90 days (3 mo) post SRS (-10 to +14 days)
History and physical with neurological exam		C ¹				C	C
Documentation of steroid use		C	C	C	C	C	C
Glucose education / supply distribution ²			R				
Fingerstick Glucose by patient			R ³	R ³	R ⁴	R ⁵	
Fingerstick Glucose by nurse/research team member			R		R	R	
Review of Medication and Glucose Logs					R	R	
CBC w/ diff and CMP including LFTs		C			C	C	C
Start Glyburide (should start at least 5 days prior to SRS)			R				
Stop Glyburide						R ⁵	
Pregnancy test (if applicable)		C					
Contrast-enhanced MRI of the brain	C ⁶					C ⁶	C ⁶
AE evaluation					C	C	C

C = Conventional Care. **R** = Research Related.

1. Baseline history and physical exam must include height and weight.
2. The patient will be supplied with a blood glucose monitor, a fingerstick glucose device, medication/blood glucose logs, and handouts for education purposes. The patient will be educated on how to measure and record blood glucose values. See Appendices II-VI.
3. Fingerstick glucose draws to be done by the patient 4 times a day (in the morning before breakfast (fasting), before lunch, before dinner, and before bed) beginning at least 5 days prior to SRS (the same day as starting glyburide) and continuing for at least 1 week after SRS.
4. Fingerstick glucose draws to be done by the patient once a day only if the patient doesn't have a concerning or serious toxicity at the 1 week post SRS visit. See Section 5.3.1 for further details.
5. The last dose of glyburide is taken on the evening of the day the 1 month post SRS MRI is done. Fingerstick glucose draws also discontinue at the same time as glyburide discontinuation.
6. MRI with and without contrast. T1-weighted, T2 and/or FLAIR MRI of the brain (maximum slice thickness 5mm). FLAIR imaging is preferred. Pretreatment MRI to be done within 21 days of SRS.

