APPENDIX VIII *continued*
STUDY SCHEDULE OF EVENTS
RANDOMIZED PORTION

Assessments	Pretreatment		Treatment		Post Treatment		
	≤ 60 days prior to registration	≤ 14 days prior to registration	5-9 days prior to SRS	Day of SRS	7 days (1 wk) post SRS (± 3 days)	30 days (1 mo) post SRS (-5 to +10 days)	90 days (3 mo) post SRS (-10 to +14 days)
History and physical with neurological exam		C ¹				C	C
Documentation of steroid use		C	C	C	C	C	C
Glucose education / supply distribution ²			R				
Fingerstick Glucose by patient			R ³	R ³	R ⁴		
Fingerstick Glucose by nurse/research team member			R		R	R	
Review of Medication and Glucose Logs					R	R	
CBC w/ diff and CMP including LFTs		C			C	C	C
Start Investigational medication (should start at least 5 days prior to SRS)			R				
Stop Investigational medication						R ⁵	
Pregnancy test (if applicable)		C					
Contrast-enhanced MRI of the brain	C ⁶					C ⁶	C ⁶
AE evaluation					C	C	C

C = Conventional Care. **R** = Research Related.

1. Baseline history and physical exam must include height and weight.
2. The patient will be supplied with a blood glucose monitor, a fingerstick glucose device, medication/blood glucose logs, and handouts for education purposes. The patient will be educated on how to measure and record blood glucose values. See Appendices II-VI.
3. Fingerstick glucose draws to be done by the patient once a day beginning at least 5 days prior to SRS (the same day as starting investigational medication) and continuing for at least 1 week after SRS. See Section 5.4.2 for further details.
4. Fingerstick glucose draws to be done by the patient may be stopped only if the patient doesn't have a concerning or serious toxicity at the 1 week post SRS visit. See Section 5.3.2 for further details.
5. The last dose of the investigational medication is taken on the evening of the day the 1 month post SRS MRI is done.

6. MRI with and without contrast. T1-weighted, T2 and/or FLAIR MRI of the brain (maximum slice thickness 5 mm). FLAIR imaging is preferred. Pretreatment MRI to be done within 21 days of SRS.

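### Stopping the drug for a concerning or serious toxicity also ends required glucose checks at once, and a footnote in the randomized schedule says the opposite

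*Combined protocol and SAP*

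**What the plan says.** **Release after a toxicity.**
- Section 4.1.6.4.1 (pilot, week 1 visit): a patient with a concerning or serious toxicity must stop glyburide "and thus can also discontinue with their fingerstick glucose draws".
- Section 4.2.6.4.1 (randomized, week 1 visit): the patient comes off the investigational medication and "thus can also discontinue with fingerstick glucose draws".
- Section 5.4.1 (pilot): a patient with a dose limiting toxicity (DLT) stops glyburide and "will not have to continue checking their blood glucose levels". Section 5.4.2.2 repeats this for the randomized portion, and section 5.4.2.3 takes it over by referring to 5.4.1.

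**Schedule of events (Appendix VIII).**
- Randomized footnote 4: patient fingersticks "may be stopped only if the patient doesn't have a concerning or serious toxicity at the 1 week post SRS visit".
- Pilot footnote 4: fingersticks are done "once a day only if the patient doesn't have a concerning or serious toxicity at the 1 week post SRS visit". It does not say what a patient with a toxicity does.
- Pilot footnote 5: "Fingerstick glucose draws also discontinue at the same time as glyburide discontinuation". Similarly, section 4.1.6.4 runs the once-daily check "until the day of discontinuation of glyburide".

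**Pharmacology.** Sections 1.4.1 and 1.4.6 give a 24-hour effect in diabetic patients. For normal subjects, 1.4.1 puts the peak level at about four hours, with drug still detectable at 24 hours. It gives no duration of effect in hours for them, only that duration scales with dose. Section 1.4.14 gives a half-life of 5 to 10 hours.

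**The concern.** The release treats the end of dosing as the end of risk. The protocol's own pharmacology does not support that: a dose taken shortly before the stop may not yet have reached its peak.

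The patient most exposed is one with asymptomatic grade 3 or 4 hypoglycemia, which Appendix VII places below 40 mg/dl and section 5.3 counts as a concerning toxicity. That patient has just shown no warning symptoms, so checks prompted by symptoms are a weak backstop. The recheck loop in 5.4.1.1 ends at the first reading of 80 mg/dl or above. After one correction, a second silent fall might go unseen. In the pilot through week 1, a patient with no toxicity checks four times a day, while one who fell below 40 mg/dl need not check at all.

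Separately, staff in the randomized portion have two opposite instructions for the same patient at the same visit. The documents do not say which governs.

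**Working it through.** **1. The two randomized rules side by side.** For a patient with a concerning or serious toxicity at week 1:
- Sections 4.2.6.4.1 and 5.4.2.2: checks may stop because there is a toxicity.
- Appendix VIII footnote 4: checks may stop only if there is no toxicity.

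The two cannot both be followed. The pilot footnotes do not contradict the pilot text in this way.

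**2. Scheduled patient fingersticks in the 24 hours after a DLT stop.** Inputs are the daily frequencies in 4.1.4.4, 4.1.5.2, 4.1.6.4, 4.2.4.5, 4.2.5.2, 5.4.1 and 5.4.2.

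| Path | Without the release | With the release |
|---|---|---|
| Pilot, through week 1 | 4 | 0 |
| Randomized under 5.4.2.2, through week 1 | 1 | 0 |
| Randomized under 5.4.2.3, through week 1 | 4 | 0 |
| Any path, after week 1 | 0 | 0 |

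The last row is zero in both columns because the pilot and 5.4.2.3 schedules end when the drug stops, and the 5.4.2.2 schedule has already ended.

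**3. Next scheduled staff fingerstick after a stop at the week 1 visit.**
- Week 1 visit: day 7 ± 3, so days 4 to 10.
- One month visit: day 30 − 5 to day 30 + 10, so days 25 to 40.
- Shortest gap: 25 − 10 = 15 days. Longest gap: 40 − 4 = 36 days.

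For a DLT before SRS, the patient is removed (7.1.4, 7.2.3). The 30-day adverse event follow-up in 7.3.3 names no glucose check.

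**4. Drug remaining after the last dose.** The formula is 0.5^(t / half-life), with the stated half-life of 5 to 10 hours.

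| Hours after last dose | Half-life 5 h | Half-life 10 h |
|---|---|---|
| 4 | 57.4% | 75.8% |
| 12 | 18.9% | 43.5% |
| 24 | 3.6% | 18.9% |
| 48 | 0.1% | 3.6% |

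This treats elimination as a single terminal phase. It describes drug level, not glucose effect, and so gives no probability of a second event.

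**The case against.** The strongest reply is that only the footnote conflict is a real defect, and that the monitoring gap is narrow and partly covered.

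- **Order of events.** Under 5.4.1, a silent low that corrects does not require a call to the study team. It would normally surface at the week 1 log review, and until then the patient stays on the full schedule. Staff take a fingerstick and a metabolic panel at that same visit. This stands and narrows the exposure to recent events. The staff reading, however, is taken at the moment of release, and a dose taken that morning may not have peaked.
- **Other safeguards.** Section 5.4.1 escalates when glucose does not recover or symptoms persist. The intervention in 5.4.1.1 includes a snack. Appendix II makes four checks a day the default unless the study team says otherwise, and prompts extra ones. These help, but Appendix II is handout advice, and none of them requires a check in the hours after a silent event that corrected.
- **Permissive wording.** The sections allow stopping and do not order it, and an investigator may continue checks. That is correct. The point is that nothing is then required.
- **Source of the 24 hours.** It comes from diabetic patients, whereas the trial excludes those on diabetes treatment. At 1.25 mg the effect may be shorter. This stands, but the protocol gives no shorter figure, and section 1.9 says oral glyburide has not been shown safe in non-diabetic people.
- **Size.** Under 5.4.2.2 the release removes one check, and some randomized patients take placebo. Both are true, but under blinding one rule must serve both arms.
- **Pilot footnote 5.** It is attached to the planned end of treatment and is weak evidence about a DLT stop. That is fair; it needs only an exception.
- **Choice of 24 hours.** Checks before meals and at bedtime leave the night uncovered, and a 10-hour half-life could argue for about 48 hours. Both stand, so 24 hours should be read as a minimum.

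**Conclusion.** The concern holds. Four sections release the patient with no minimum interval, and randomized Appendix VIII footnote 4 contradicts two of them. The contradiction is wrong as written and rests on no assumption. The monitoring gap is a cheap safety improvement worth making. It rests on the drug possibly still acting in non-diabetic patients for some hours after the last dose, which the stated peak time, half-life and 24-hour detectability make plausible but do not prove.

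The measurable effect is confined to the period through week 1, as counted above. The wider gap after week 1 comes from the schedule itself, which is why the remedy must also allow checks to resume. Confidence is medium, because several partial safeguards exist and the documents offer nothing from which to estimate recurrence.

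**What to change.** In 4.1.6.4.1, 4.2.6.4.1, 5.4.1 and 5.4.2.2, replace the release with:

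> After a concerning or serious toxicity, continue (or resume) fingersticks before meals and at bedtime for at least 24 hours after the last dose and until glucose is documented at 80 mg/dl or above, then stop.

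Reword randomized Appendix VIII footnote 4 to:

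> May be stopped at the 1 week visit if there is no concerning or serious toxicity; otherwise stop only after the 24-hour post-dose checks.

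Add the same exception to 4.1.6.4 and to pilot footnotes 4 and 5. Section 5.4.2.3 follows through its reference to 5.4.1. Leave the DLT window and the planned end-of-treatment stop unchanged.

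The cost is wording in four sections, 4.1.6.4 and three footnotes, plus about 4 fingersticks per patient with a DLT on the meter already supplied. In the pilot that is 4 × 5 = 20 if five patients have a DLT and 4 × 10 = 40 if all ten do. Through week 1 in the pilot, it only keeps the existing schedule going for one more day. Logs can be collected at the one month visit. Patients removed before SRS can report readings in the existing 30-day follow-up. The only downside is the extra fingersticks.

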4.1.9 Conditions for early patient stopping of glyburide

- 4.1.9.1** A dose limiting toxicity (DLT) is reached. See section 5.3.1.
- 4.1.9.2** Patient requires corticosteroid administration after registration but prior to SRS, please note these patients will be deemed inevaluable.

4.2 Randomized Portion

4.2.1 Within 60 days prior to registration

- 4.2.1.1** Contrast-enhanced MRI of the brain (may be performed at an outside institution).

4.2.2 Within 14 days prior to registration

- 4.2.2.1** History and Physical with height, weight, neurological exam and corticosteroid use documentation. If using dexamethasone (or any other corticosteroid with the purpose of treating cerebral edema), must implement a plan to have this safely discontinued by 5 days prior to SRS.

- 4.2.2.2** Complete Blood Count (CBC) with differential and a Comprehensive metabolic panel (CMP) including Liver Function Tests (LFTs).
- 4.2.2.3** Pregnancy test for women of child-bearing potential.

4.2.3 Within 21 days prior to SRS

- 4.2.3.1** Follow-up brain MRI with and without contrast. T1-weighted, T2, and/or FLAIR MRI of the brain (maximum slice thickness 5mm). FLAIR imaging is preferred.
 - 4.2.3.1.1** T1 post gadolinium sequence will be imported into the Eclipse treatment planning system and the radiation oncologist (who will be blinded to the patient's investigational medication) will contour the enhancing tumor that received the prescribed dose of SRS.
 - 4.2.3.1.2** FLAIR sequence will be imported into the Eclipse treatment planning system. FLAIR volume will be automatically calculated using "Region Growing" on Eclipse (Appendix I). The automated contours will be verified and modified as needed by the radiation oncologist who will be blinded to the patient's investigational medication.

4.2.4 5-9 days prior to SRS

- 4.2.4.1** Randomization will occur (can be any time after registration/study entry and up until 5-9 days prior to SRS).
- 4.2.4.2** Documentation of corticosteroid use/no dexamethasone (or any other corticosteroid with the purpose of treating cerebral edema) use.
- 4.2.4.3** Give patient a sufficient supply of investigational medication: either non-micronized Glyburide tablets (1.25 mg) or placebo, to be taken orally twice a day (in the morning with breakfast and in the evening with dinner). Missed doses will not be made up. Patient, physicians, and the study team will be blinded to the investigational medication. Patient should be instructed to begin investigational medication at least 5 days prior to SRS and continue investigational medication until the evening dose of the one month post SRS MRI scan.
- 4.2.4.4** Provide patient with study supplies that include a medication/blood glucose log (for recording time of taking the investigational medication as well as time and value of blood glucose draws), a blood glucose monitor, and handouts for education purposes. The patient will be educated on how to measure and record blood glucose values (see Appendices II-VI).
- 4.2.4.5** Patient should begin fingerstick glucose draws once a day beginning the day of investigational medication initiation (in the morning before breakfast [fasting]). Please see section 5.4.2 for further details. An additional fingerstick glucose draw will be taken by the nurse/research team member at this visit.

